- i. Toxicity will be graded according to the NCI-CTC for application in adverse event reporting. The NCI-CTC has been reviewed specifically for this protocol and is appropriate for this study population. The purpose of using the NCI-CTC system is to provide standard language to describe toxicities, and to facilitate tabulation and analysis of the data and assessment of the clinical significance of treatment-related toxicities. The investigator will try to determine the relationship of toxicity to baked milk immunotherapy as not related, possibly related, or definitely related using standard criteria for clinical trials. All grades of toxicity will be noted. Toxicity grades are assigned by the study site to indicate the severity of adverse experiences and toxicities.
- ii. Adverse events, not included in the NCI-CTC listing, should be recorded and graded 0-4 according to the General Grade Definition provided below:

Table 7: General Grade Definitions

| Grade 0 | Mild | Transient or mild discomforts (< 48 hours), no or |
|---------|-----------------|--|
| | | minimal medical intervention/therapy required, |
| | | hospitalization not necessary (non-prescription or single- |
| | | use prescription therapy may be employed to relieve |
| | | symptoms, e.g., aspirin for simple headache, |
| | | acetaminophen for postsurgical pain) |
| Grade 1 | Moderate | Mild to moderate limitation in activity, some assistance |
| | | may be needed; no or minimal intervention/therapy |
| | | required, hospitalization possible. |
| Grade 2 | Severe | Marked limitation in activity, some assistance usually |
| | | required; medical intervention/therapy required |
| | | hospitalization possible. |
| Grade 3 | Lifethreatening | Extreme limitation in activity, significant assistance |
| | | required; significant medical/therapy intervention |
| | | required hospitalization or hospice care probable. |
| Grade 4 | Death | Death |

iii. Adverse Event Reporting:

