Within the context of this study, blood draws, allergy skin prick tests, dose increases and oral food allergy challenge tests will be observed and recorded. Adverse events (AEs) that are temporally related to these procedures or to home dosing with the study medications (during 3 days following the procedure) will be reportable adverse events. Anticipated local reactions to prick skin tests and oral food challenges reactions occurring during the challenge procedure will not be additionally reported on an adverse event form unless the reaction results in a serious adverse event. In that case it will be reported both on the reaction form and on a serious adverse event form.

The following events would be considered expected events for the procedures being performed:

- Blood draw: nausea and vomiting, local infection, and fainting
- Prick skin test: Pruritus, transient hive, systemic allergic reaction
- Oral food challenges and dosing with study medications: allergic reactions related to the skin (hives, pruritus, eczema flare), the respiratory tract (nasal congestion, rhinorrhea, fits of sneezing, difficulty breathing, asthma), and the GI tract (oropharyngeal pruritus and edema, nausea, vomiting and diarrhea).

All "unanticipated" adverse events related to the experimental procedures will be reported to the DSMB in an expedited manner if they are Grade 2 and above in severity. All "anticipated" adverse events related to the experimental procedures will also be reported in an expedited manner if they are Grade 2 and above in severity. Subject deaths are reportable within 24 hours. The investigator will continue to follow or obtain documentation of the resolution course of such an event. A copy of the annual report of adverse events will be reported to the IRB.

iv. Data and Safety Monitoring:

A Data Safety Monitoring Board will be convened for overview of this study. The Principal Investigator and Co-Investigators are responsible for collecting and recoding all clinical data. As these results are collected, all toxicities and adverse events will be identified and reported to the PI. Adverse events will be reported as described above. The Principal Investigator will determine the relationship of the event to the study intervention and decide the course of action for the study participant.

Yearly reports will be made to the DSMB and proper Institutional Committees, as required. All adverse events will be kept in a computerized file by numerical identifier.

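### A related event outside the NCI-CTC listing that is graded moderate but leads to admission has no stated expedited route to the DSMB

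*Combined protocol and SAP*

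**What the plan says.** Section 8.c.i makes the NCI-CTC the main scale: "Toxicity will be graded according to the NCI-CTC for application in adverse event reporting". Section 8.c.ii adds a second scale for whatever that listing does not cover: "Adverse events, not included in the NCI-CTC listing, should be recorded and graded 0-4 according to the" General Grade Definitions printed below it. In that table mild is Grade 0, moderate Grade 1, severe Grade 2, life-threatening Grade 3 and death Grade 4. The Grade 1 entry begins "Mild to moderate limitation in activity, some assistance" and ends "required, hospitalization possible".

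Section 8.c.iii sets one numeric threshold for prompt reporting. Unanticipated events related to the study procedures "will be reported to the DSMB in an expedited manner if they are Grade 2 and above in severity". Anticipated related events have the same threshold. Deaths are reportable within 24 hours. Section 8.c.iv otherwise provides for yearly reports to the DSMB.

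**The concern.** A threshold given as a bare number works only if the number has one meaning and if everything the board would want quickly lies at or above it. Here the number is applied to two scales, and the text neither says which is meant nor shows that they agree. On the protocol's own scale, the grade just below the threshold is one at which admission to hospital is contemplated.

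The point is prompt oversight. Safety is the primary outcome, and the participants are children chosen because they react to small amounts of baked milk. An event that leads to the admission of a child in such a trial is one that a safety board would ordinarily expect to see promptly. As written, whether it does can turn on whether the event term is listed and whether the investigator calls it moderate or severe.

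**Working it through.** No sample size, power or error rate is involved, so the check is to lay the grade table against the reporting rule and then look for another rule that would catch what falls through.

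**Step 1. The protocol's table against the Grade 2 threshold (Sections 8.c.ii and 8.c.iii), for a related event outside the NCI-CTC listing.**

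| Grade | Label | What the table says about hospital | Expedited if related? |
|---|---|---|---|
| 0 | Mild | not necessary | No |
| 1 | Moderate | possible | No |
| 2 | Severe | possible | Yes |
| 3 | Life-threatening | probable | Yes |
| 4 | Death | not applicable | Yes, within 24 hours |

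Two of the five grades fall below the threshold, and one of those two allows for admission.

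**Step 2. How wide the gap is.** Grade 1 requires that little or no therapy is needed, whereas Grade 2 applies once medical intervention is required. Most admissions for treatment would therefore be Grade 2. Section 8.b.i also provides for hospitalisation after a challenge or the initial escalation when severe systemic symptoms do not resolve. Those would be severe on this table, hence Grade 2 and expedited if related. What remains is an event that meets four conditions: related, unlisted, judged moderate with minimal therapy, and nonetheless admitted, for instance for observation.

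**Step 3. Other routes that might catch it.**

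- *Serious adverse event route.* Section 8.c.iii mentions a serious adverse event form for skin-test and challenge reactions. It gives no definition of a serious event, no timeline and no DSMB recipient. Section 7.c analyses serious adverse events but does not define them either.
- *Suspension rules.* Section 7.d lists four: any death, more than one severe anaphylactic reaction to dosing, more than three subjects needing more than one epinephrine injection during dosing, and the first five subjects failing to reach 3 mg. None of the four names hospitalisation.
- *Routine reporting.* Section 8.c.iv gives a yearly cycle. Adverse events reach the principal investigator as they are collected, but that is not a report to the board.

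None of these is a stated expedited route for the event in Step 2.

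**Step 4. Consistency with the rest of the protocol.** The exclusion criteria in Section 5 count a reaction at the qualifying challenge as severe if it needs an overnight stay in hospital. Section 8.c.ii allows admission under moderate. Within Grade 1 itself, minimal need for therapy sits beside possible admission. These passages must be reconciled.

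**The case against.** The best defence is that the gap is small and other safeguards surround it. Grade 1 is confined to events needing little or no therapy. The hospitalisation pathway that the protocol actually describes leads to Grade 2. Section 7.d brings in expedited IRB and DSMB review for the most dangerous patterns. All of this stands and limits the size of the point. It does not close the gap, because none of these provisions mentions an admitted event graded moderate.

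Three stronger readings are tempting, and the documents do not support them.

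- A reader might infer that the same severity is handled differently depending on the scale. That needs the NCI-CTC grade labels, which the protocol does not print. If that scale were numbered like the protocol's table, there would be no mismatch. All that can be said is that alignment is not shown.
- A reader might try to size the problem from the 47% moderate-reaction rate in Section 8.a.i. That figure comes from unheated milk in 2-3-year-olds and covers reactions such as vomiting, wheezing and urticaria. Nothing in the documents suggests that these are missing from the NCI-CTC listing, which Section 8.c.i says was reviewed for this protocol and found suitable.
- A reader might infer that the primary analysis is compromised. Section 7.c analyses numbers of adverse events, and serious events by subject and by dose. It specifies no analysis by grade, so no listed comparison depends on the numbering.

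**Conclusion.** The point holds in a narrow form. As written, a related event outside the NCI-CTC listing that is judged moderate, needs little or no therapy and still leads to admission has no stated expedited route to the DSMB. It could wait for the yearly report. Separately, the Grade 2 trigger is ambiguous because it does not name its scale.

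The size cannot be put as a count: the documents do not show which events are unlisted or how often a moderate event would lead to admission. Such events are probably rare. The conclusion rests on the printed grade table, the printed threshold and the absence of a hospitalisation criterion elsewhere. It needs no assumption about NCI-CTC numbering. It is worth correcting because the trial's primary outcome is safety and the correction is cheap. It is a weakness in oversight, not a flaw in the planned comparisons.

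**What to change.** Make three changes to Section 8.c.

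1. Extend the expedited-reporting trigger in 8.c.iii to any related event involving hospitalisation, whatever its grade. This closes the gap regardless of how the two scales compare.
2. State the trigger by severity label as well as by number, so that it reads the same for listed and unlisted events.
3. Name the NCI-CTC version in use and check the General Grade Definitions against it. Renumber the protocol's table only if the two do not align.

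In the same revision, reconcile the Grade 1 hospitalisation wording with the definition of a severe challenge reaction in Section 5.

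The cost is protocol and form wording, and possibly a few more expedited reports. If the check in item 3 showed a mismatch, unlisted events already recorded would also need regrading. No dose, schedule, clinical rule or planned analysis changes.

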| Week | -3 | -2 | -1* | 0 | 2 | 4 | 6 | 8 | 10 | 12 | 14 | 16 | 18 | 20 | 22 | 30 | 38 | 46 | 52 | 54* |
| Visit Number | 1 | 2 | 3 | 4 | 5 | 6 | 7 | 8 | 9 | 10 | 11 | 12 | 13 | 14 | 15 | 16 | 17 | 18 | 19 | 20 |
| Informed Consent | х | | | | | | | | | | | | | | | | | | | |
| History | Х | | | | | | | | | | | | | | | | | | | |
| Limited physical | | | | | | | | | | | | | | | | | | | | |
| exam | х | х | x | х | Х | х | х | х | x | х | х | x | x | x | x | x | x | x | x | x |
| Vital Signs | х | х | х | х | Х | х | х | х | х | х | х | х | х | х | х | х | х | х | х | х |
| Symptom/diet | | | | | | | | | | | | | | | | | | | | |
| information | Х | | | Х | Х | Х | х | Х | х | х | х | х | х | Х | х | х | х | х | Х | Х |
| U HCG | х | x | | X | Х | | х | | х | | х | | х | | х | х | х | х | х | |
| Spirometry ⁺ | x | | | | | | | | | | | | | | | | | | | |
| Peak Flow Rate ⁺ | х | х | х | х | Х | х | х | х | х | х | х | х | х | х | х | х | х | х | х | х |
| SPT | x | | | | | | | | | | | | | | | x | | | х | |
| Blood draw | X | | | | | | | | | | | | | | | X | | | х | |
| QOL Questionnaire | Х | | | | | | | | | | | | | | | | | | x | |
| GI assessment | Х | | | х | | х | | х | | x | | х | | x | х | x | x | x | x | |
| DBPCFC #1 | | х | х | | | | | | | | | | | | | | | | | |
| DBPCFC #2 | | | | | | | | | | | | | | | | | | | х | х |
| Randomization | | | x | | | | | | | | | | | | | | | | | |
| OIT dose increase | | | | x | X | x | x | x | x | х | x | x | х | х | х | | | | | |

*Second half of food challenge must occur within 21 days of the first half of the challenge ⁺ Spirometry will be attempted in all subjects ≥ 6 years old. Peak Flow rate will be attempted for children < 6 years old.

Table 9: Study Year 2 -4 schedule: Initial Treatment Group who Achieved 2 grams during Year1

| | | | | | | DBF | CFC | DBPCFC#4 ⁺ | |
|-----------------------|----|--------|-------|-------|-----|-----|------|-----------------------|------|
| | 1 | Mainte | nance | Phase | #2 | # | 43 | | 1 |
| Week | 56 | 68 | 80 | 92 | 104 | 106 | 108* | 110 | 112* |
| Visit Number | 21 | 22 | 23 | 24 | 25 | 26 | 27 | 28 | 29 |
| Informed Consent | | | | | | | | | |
| History | | | | | | | | | |
| | | | | | | | | | |
| Limited physical exam | x | x | х | x | Х | x | х | x | Х |
| Vital Signs | х | х | х | х | Х | х | х | х | Х |
| Symptom/diet | | | | | | | | | |
| information | x | х | х | x | Х | x | х | х | Х |
| | ~ | х | х | х | Х | х | | х | |
